# Statistical Analysis Plan (SAP)

---

Study Title: Evaluating the Impact of the Entrepreneurship School with Gender Lens (ESGL) on Self-Reliance and Wellbeing among Forcibly Displaced Women in Colombia

Study Type: Pilot Randomized Controlled Trial (RCT)

Version: April 2024

## 1. Objectives

- To assess the impact of the ESGL intervention on household self-reliance, depressive symptoms, and resilience.
- To estimate both the intent-to-treat (ITT) and the local average treatment effect (LATE) of the intervention using instrumental variable analysis.
- To explore the role of participant characteristics in loss to follow-up and outcome changes.

## 2. Primary Outcomes

- Self-reliance: Total and domain-specific scores from the Self-Reliance Index (SRI), with scores ranging from 1 to 5 (except health status domain: 1–3).
- Depression: Patient Health Questionnaire-9 (PHQ-9), scores range 0–27; higher scores indicate more severe depressive symptoms.
- Resilience: Brief Resilient Coping Scale (BRCS), scores range 4–20; higher scores indicate greater coping ability.

## 3. Study Sample

Participants were randomized within each of three cities to the treatment or control group. Inclusion was restricted to women scoring between 2.0 and 4.25 on the SRI at baseline. Additional inclusion criteria included: being a woman at least 18 years of age; at risk of or had ever experienced gender-based violence; Colombian or Venezuelan (with a Temporary Protection Permit); resided in Colombia for at least six months; and had an entrepreneur profile assessed through HIAS' profile scanning process.

## 4. Descriptive and Baseline Analysis

- Baseline Balance: Descriptive statistics will be computed separately by study arm. Mean comparisons will be conducted using independent samples t-tests.
- Imbalance Adjustment: Outcomes found to differ significantly at baseline between groups will be included as controls in regression models of change scores.

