The Self-Reliance Index (SRI) is the first-ever global tool for measuring the progress of refugee households toward self-reliance (Seff, Leeson, and Stark, 2021). The tool contains twelve domains focused on a household's basic needs, resources, and sustainability. Domains measure conditions and assets that increase the likelihood that refugees will be able to continue meeting their needs in the future. The study participant will respond on behalf of her household. The final self-reliance score may take a value from 1 to 5, with higher scores reflecting greater self-reliance. The tool is available in Spanish and has been previously validated with Venezuelan migrants in Colombia.

Resilience:

The Brief Resilient Coping Scale (BRCS) captures tendencies to cope adaptively with stress. The scale focuses on the tendency to effectively use coping strategies in a flexible and committed manner to actively solve problems despite stressful circumstances (Trejos Herrera et al., 2023).

Women's empowerment

Women's empowerment will be measured using the Women's Multidimensional Empowerment Index, which was developed using the 2015 Colombian Demographic and Health Survey (Rodríguez Guerrero, Nimeh, & Franco Correa, 2021). The index assesses empowerment multidimensionally based on the definition of empowerment proposed by Kabeer (1999) (Resources, domestic decision making, decision making on personal matters, and achievements), while capturing the notion of disempowerment.

Gender-based violence: Three items from the HIAS Knowledge and Perception of GBV risks and Women's Empowerment tool will be used. The HIAS tool was adapted based on other tools used in the Latin American region (cite). The three items pertain to self-reported perceptions of feeling supported by the community, feeling useful, and feeling controlled by one or more people. Responses are on a likert scale.

Ethical considerations

Risks and Benefits

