## 5. Estimating Treatment Effects

### 5.1. Intent-to-Treat (ITT) Analysis

OLS regression models will estimate the average treatment effect of assignment to the treatment group on changes in each outcome.

Models:

1. Bivariate association between treatment assignment and outcome change.
2. Model 1 + controls for baseline value of outcome.
3. Model 2 + controls for baseline covariates associated with outcome of interest at baseline.

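### SAP section 4 lets a baseline significance test between randomised arms choose covariates, and the rule is not reconciled with the section 5.1 models, none of which is named primary

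*SAP*

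**What the plan says.** SAP section 4 compares the arms at baseline: "Mean comparisons will be conducted using independent samples t-tests". It then makes adjustment depend on the result: "Outcomes found to differ significantly at baseline between groups will be included as controls in regression models of change scores". No significance level is given for these tests.

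SAP section 5.1 lists three OLS models for the change in each outcome:

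- Model 1: "Bivariate association between treatment assignment and outcome change".
- Model 2: "Model 1 + controls for baseline value of outcome".
- Model 3: "Model 2 + controls for baseline covariates associated with outcome of interest at baseline".

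None of the three refers to a between-arm test, and none is called primary. Section 5.2 estimates the effect of adherence on outcome changes by two-stage least squares and lists no covariates. Section 7 adds an endline model that controls for baseline values without condition.

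Section 2 counts both total and domain scores of the Self-Reliance Index (SRI) as primary outcomes, with PHQ-9 and BRCS. On the SRI, the protocol states: "The tool contains twelve domains". The outcomes open to the baseline test therefore number 3 (totals only) or 15 (SRI total, 12 domains, PHQ-9, BRCS).

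**The concern.** The protocol randomises after baseline data are collected. Under sound randomisation any baseline difference is due to chance, so a p-value for that difference measures the luck of the draw. What makes a covariate worth including is how strongly it predicts the outcome, and the test does not measure that. A weak predictor enters if it happens to differ, and a strong one stays out if its imbalance falls just short.

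The rule also leaves the specification open. Every model in section 5.1 regresses a change score, so on a literal reading a flagged outcome would enter all of them. Model 1 would stop being bivariate, and Models 2 and 3 would gain baselines of other outcomes. If section 4 is instead meant only as background to Model 2, the two sections overlap without saying so. Either way, an analyst cannot tell which covariates belong in which model until the baseline tests have been run.

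**Working it through.** The documents give no power, effect size, SD or alpha for this point, so there is no stated figure to reproduce. What follows is an illustration.

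**Inputs from the documents.** 80 women per city and 2:1 allocation (Protocol, recruitment section). Three cities (SAP section 3) give N = 240, split 160:80. Four cities (Protocol) would give N = 320.

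**Assumptions not in the documents.** Two-sided alpha 0.05, normal outcomes with equal baseline and endline SDs, pre-post correlation ρ of 0.3, 0.5 or 0.7, no attrition. Results are in SD units.

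**1. How often the test flags something by chance.** With independent tests, 1 − 0.95^3 = 14.3% for three outcomes and 1 − 0.95^15 = 53.7% for fifteen. SRI domains are correlated with each other and with their total, so the second figure is an upper guide.

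**2. What escapes the test.** The SE of a baseline difference is √(1/160 + 1/80) = 0.137. The largest unflagged imbalance is 1.96 × 0.137 = 0.27 SD at N = 240. At N = 320 it is 1.96 × 0.1186 = 0.23 SD.

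**3. What an unflagged imbalance does to Model 1.** A change score without baseline adjustment shifts by (1 − ρ) × imbalance. At the threshold:

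| ρ | N = 240 | N = 320 |
|---|---|---|
| 0.3 | 0.188 | 0.163 |
| 0.5 | 0.134 | 0.116 |
| 0.7 | 0.081 | 0.070 |

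Model 2 removes this shift.

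**4. Type I error** (simulation, 20,000 trials, 160:80, no effect; the rule is applied to the outcome's own baseline in Model 1):

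| ρ | Model 1 + rule, all trials | Model 1 + rule, unflagged imbalance above 0.2 SD | Model 2, same trials |
|---|---|---|---|
| 0.3 | 4.0% | 11.5% | 4.9% |
| 0.5 | 4.0% | 9.5% | 5.3% |
| 0.7 | 4.9% | 8.8% | 5.1% |

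The third and fourth columns rest on the 9.1 to 9.4% of trials with such an imbalance, about 1,850 runs each, so the third has a simulation SE of about √(0.10 × 0.90 / 1,850) = 0.7 points. A closed-form check agrees. Given imbalance d, the Model 1 estimate has mean −(1 − ρ)d and SD √(1 − ρ²) × 0.137, and it is tested against 1.96 × √(2(1 − ρ)) × 0.137. At the average such imbalance, d = 0.23, the rejection rates are 11.5%, 9.9% and 8.0%.

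**5. Power for a true effect of 0.3 SD** (simulation, 160:80):

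| ρ | Model 1 alone | Model 1 + rule | Baseline always adjusted |
|---|---|---|---|
| 0.3 | 45% | 46% | 62% |
| 0.5 | 59% | 60% | 71% |
| 0.7 | 80% | 81% | 86% |

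The SEs explain the last column: 0.162, 0.137 and 0.106 for the unadjusted change score, against 0.131, 0.119 and 0.098 with baseline adjustment.

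**6. Section 5.2.** With one binary instrument and no covariates, 2SLS equals the Model 1 estimate divided by the between-arm difference in adherence. It inherits the shift in step 3, enlarged by that division. If section 4 governs these regressions, its rule is the only stated way an outcome's own baseline could enter them.

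**The case against.** The strongest reply is that the SAP already does most of what is needed. Model 2 always includes the outcome's own baseline, usually its strongest predictor. Model 3 builds on Model 2, and the section 7 model also controls for baseline. The section 4 sentence may be no more than a prose rationale for Model 2. This stands, and it limits the point. A reader might infer that every model's covariates depend on chance, or that imbalances below the threshold go uncorrected throughout. Section 5.1 does not support that for an outcome's own baseline in Models 2 and 3.

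Two further inferences are tempting and also fail. One is that the rule costs the power difference in step 5. It does not: Model 1 with the rule is about one percentage point better than Model 1 without it. The gap comes from leaving a change score unadjusted, and deleting the rule alone would recover none of it. The other is that the rule inflates type I error. Overall it is at or slightly below 5%; the excess appears only conditionally on a sizeable unflagged imbalance.

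The reply does not explain how section 4 and section 5.1 combine, does not identify a primary model, and does not reach section 5.2, which has no equivalent of Model 2.

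**Conclusion.** The concern holds in a limited form. Section 4 chooses covariates by chance imbalance, and the SAP does not say how that choice interacts with its own models. The exposure is confined to three places: Model 1, the 2SLS models, and baselines of other outcomes that may be added by chance.

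In those places the rule does not deliver the protection it appears to offer. It leaves power almost where plain Model 1 puts it. It also gives no protection in the roughly 9% of trials where an imbalance is sizeable but unflagged; there the false-positive rate is about 9 to 11%, against about 5% with unconditional adjustment. These sizes rest on the assumed alpha, correlations, equal SDs, 160:80 split and absence of attrition. The argument that a between-arm test is the wrong selector needs none of them.

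This should be changed. It does not undermine Model 2 or Model 3 as adjustments for the outcome's own baseline.

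**What to change.** - Delete the Imbalance Adjustment rule from section 4, and state that nothing in the baseline table changes any model.
- In section 5.1, name Model 2 as the primary ITT analysis for every outcome, adjusting for that outcome's own baseline whatever the observed balance. For each SRI domain, use that domain's baseline.
- Keep Model 1 as an unadjusted descriptive result, labelled as such.
- In section 5.2, put the same baseline covariate in both stages of the 2SLS.
- If baselines of the other primary outcomes are wanted as covariates, list them in advance and use the same list regardless of balance. Model 3's covariates likewise need a list fixed in advance if it is to be more than exploratory.

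The cost is a few sentences of SAP wording and one degree of freedom per model. No new data are needed, because every baseline score is already collected before randomisation.

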## 5. Estimating Treatment Effects

### 5.1. Intent-to-Treat (ITT) Analysis

OLS regression models will estimate the average treatment effect of assignment to the treatment group on changes in each outcome.

Models:

1. Bivariate association between treatment assignment and outcome change.
2. Model 1 + controls for baseline value of outcome.
3. Model 2 + controls for baseline covariates associated with outcome of interest at baseline.

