As of August 2021, Colombia hosts the vast majority of Venezuelan refugees and migrants (UNHCR, 2022). For vulnerable refugees and migrants in Colombia, and especially for women, gender-based violence (GBV) is present during transit and continues in their new homes where xenophobia, lack of accessible and adequate services, lack of safe economic opportunities, and lack of information on access to services, further increase risk. Lack of livelihood opportunities also affect vulnerable refugees and migrants, especially women, with barriers to employment including lack of information; precarious working conditions with lower payments and longer working days with increasing risks of labor exploitation; xenophobia and discrimination; limited access to formal labor markets; lack of access to financial services, among others. To address these issues, we are conducting a randomized-controlled trial (RCT) of HIAS' Entrepreneurship School with Gender Lens (ESGL), a methodology that targets GBV survivors and women at-risk to help them develop business ideas, access needed support for the prevention of and response to GBV, exploitation and trafficking, and improve participants' overall self-reliance. The RCT will be conducted within four cities in Colombia; approximately 80 eligible participants will be enrolled in each city and randomized to a treatment or control arm in a 2:1 ratio. Survey questionnaires will be administered to participants at baseline, eight months following baseline (endline), and 3-4 months after endline. Outcomes of interest include household self-reliance, mental health, empowerment, decision-making, and GBV risk and knowledge.

Background and Rationale

Colombia is a major host of forcibly displaced Venezuelans, currently with approximately 2.5 million vulnerable refugees and migrants. Colombia also has over 6.7 million internally displaced persons (IDPs) due to historical conflicts and violence. For vulnerable refugees and migrants in Colombia, GBV is present during transit and continues in their new homes where xenophobia, lack of accessible and adequate services, lack of safe economic opportunities, and lack of information on access to services, further increase risk.

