Participants will be recruited from four cities: Cali, Ipiales, Pasto, and Popayan. The study will aim to enrol 80 women in the study within each city, where participants will be randomly assigned to the intervention or control arm at a 2:1 ratio.. As such, 90-100 women will be identified as potential participants through the pre-screening tool to account for ineligibility during the SRI administration phase.

At the time of enrolment, participants will receive a unique study ID. Following enrolment and baseline data collection, participants will be randomly assigned to the control or treatment arm using a random number generator in Stata (a data analysis software). The unique study ID will be used to track participants over time for future points of data collection.

Consent

Prior to data collection, the researcher will explain the study purpose, procedures, potential risks, and safeguards, such as participant confidentiality and referrals for services, where necessary. The researcher will explain that participants may be assigned to take part in the intervention based on randomization but that non-selection for the intervention will not prevent them from later participation in HIAS programs. They will be informed that they may also be provided with a referral for other programs. The researcher will emphasize that participation is completely voluntary and that participants will not be penalized in any way for choosing not to participate. Researchers will also explain and emphasize that participating or not participating in the study is purely voluntary and will have no impact on their access to future HIAS programming. Prospective participants will also be told that they are free to withdraw from the study at any time and to refuse to answer some or all of the questions. Participants will be informed that their data may be used by the research team in the future. The researcher will encourage the interviewee to ask any questions about the study processes before consenting to participate in the study.

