### 5.2. Instrumental Variable (IV) Analysis

Participants are considered to have adhered to the intervention if they received both a completion certificate and seed capital.

Two-stage least squares (2SLS) using `ivregress 2sls` in Stata.

Stage 1: Predict adherence using treatment assignment as an instrument.

Stage 2: Estimate the causal effect of adherence on outcome changes.

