## 7. Sensitivity Analyses

Compare results using:

- Change scores vs. endline-only models controlling for baseline values.

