## 8. Software

All analyses will be conducted in Stata (version 16), using appropriate packages for regression, 2SLS, and multiple imputation.

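### SAP 5.1 and 5.2 name no variance estimator for OLS or 2SLS; under 2:1 allocation the default pooled standard errors are not protected against unequal arm variances, and one line would fix this

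*SAP*

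**What the plan says.** SAP 5.1 states: "OLS regression models will estimate the average treatment effect of assignment to the treatment group on changes in each outcome". It lists three models (bivariate, plus baseline value, plus covariates) and says nothing about standard errors. SAP 5.2 states: "Two-stage least squares (2SLS) using `ivregress 2sls` in Stata". The routine is named without options.

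The other places where a variance estimator might appear do not supply one. SAP 8 reads "All analyses will be conducted in Stata (version 16), using appropriate packages for regression, 2SLS, and multiple imputation". The only sensitivity analysis, in SAP 7, is "Change scores vs. endline-only models controlling for baseline values".

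The allocation ratio is in the protocol only. Under the recruitment and sample size heading, "participants will be randomly assigned to the intervention or control arm at a 2:1 ratio", and the opening summary says the same. SAP 3 says "Participants were randomized within each of three cities to the treatment or control group" and gives no ratio. The protocol's data analysis section plans random coefficient models instead, also without a statement on variance by arm.

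**The concern.** The default standard error for OLS, and for 2SLS, uses a single residual variance for everyone. With equal arms the estimated standard error of the treatment contrast is still right when the arms differ in spread, because the two errors cancel. With 2:1 allocation they do not. The pooled variance is weighted towards the larger, treated arm, while the smaller control arm contributes more to the true uncertainty.

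Some difference in spread is plausible. Seed capital goes only to women who complete training and pitch, so the treated arm mixes funded and unfunded women, and businesses may do unevenly well. In the other direction, the outcome scales are bounded (SRI 1-5, PHQ-9 0-27), and movement towards a bound could narrow the treated arm. The documents do not say which applies to which outcome.

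At stake are the confidence intervals and p-values of every ITT and 2SLS estimate. If the estimator is left open, the choice between default and robust errors could also be made after the results are known.

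**Working it through.** **Inputs.** Allocation 2:1 (protocol). The protocol states "The study will aim to enrol 80 women in the study within each city" and names four cities: 4 × 80 = 320, about 213:107. SAP 3 has three cities and gives no N. At 80 per city that is 240, or 160:80 (assumption). The documents give no SD, standard error, alpha or power, so there is no figure of the plan to reproduce. The variance ratio r = treated/control is therefore an assumption, shown as a range.

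**Formula.** For a two-arm contrast:
- default SE² = pooled variance × (1/n_T + 1/n_C)
- true SE² = v_T/n_T + v_C/n_C

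At 2:1, default SE / true SE = √[(2r + 1)/(r + 2)]. At 1:1 the ratio is 1 for every r.

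| r | default/true SE | error in SE | size of a nominal 5% test |
|---|---|---|---|
| 0.5 | √(2/2.5) = 0.894 | 10.6% too small | 8.0% |
| 0.75 | √(2.5/2.75) = 0.953 | 4.7% too small | 6.2% |
| 1 | 1 | none | 5% |
| 1.5 | √(4/3.5) = 1.069 | 6.9% too large | 3.6% |
| 2 | √(5/4) = 1.118 | 11.8% too large | 2.8% |

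The last column is 2{1 − Φ(1.96 × ratio)}. The result hardly depends on N: at r = 2 the ratio is 1.118 for N = 320 and 1.119 for N = 240; at r = 0.5 it is 0.895 and 0.894.

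**What the funded/unfunded mixture alone implies.** Suppose a proportion p adheres and gains d control-group SDs, the others gain nothing, and the gain is unrelated to the change a woman would have had anyway. Then r = 1 + p(1 − p)d². With p = 0.75, p(1 − p) = 0.1875:
- d = 0.5: r = 1.047, ratio √(3.094/3.047) = 1.008, so 0.8% too large.
- d = 1: r = 1.188, ratio √(3.375/3.188) = 1.029, so 2.9% too large.
- r = 2 would need d = √(1/0.1875) = 2.3 SD.

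At p = 0.5, where the mixture is greatest, the errors are 1.0% (d = 0.5) and 3.8% (d = 1). These figures are for the ITT contrast. In 2SLS the residual subtracts the adherers' gain, so a gain equal for all adherers adds no variance difference there; only a varying gain does.

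**Simulation.** N = 240 (160:80), 6,000 replicates per scenario, no effect on the mean, 70% adherence in the treated arm and none in control, and a baseline covariate unrelated to the outcome.

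| Model | default SE / empirical SD, r = 2 | same, r = 0.5 |
|---|---|---|
| OLS, bivariate | 1.119 | 0.890 |
| OLS plus baseline | 1.117 | 0.890 |
| 2SLS | 1.114 | 0.890 |

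With heteroskedasticity-robust errors (HC1), the ratio was 0.99 to 1.00 and rejection 4.8% to 5.2% in all three models at both values of r.

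**The case against.** The SAP is silent; it does not prescribe equal-variance errors. OLS is a point estimator compatible with robust errors, and SAP 5.2 names a routine, not a full command line. This stands. A reader might infer that the SAP has committed itself to wrong standard errors, but the documents show only that nothing but the default has been specified.

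A reader might also infer that the standard errors will be about 11% off. The documents do not support that. They contain no arm-specific SDs, and the one mechanism that can be put into figures, the mixture, gives about 1-3% at 75% adherence, in the conservative direction. Nothing in the documents shows that controls vary twice as much as treated women, which is what an 11% understatement needs.

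Nor do the documents support a claim that the trial has an 8% type I error. If the programme does nothing for anyone, randomisation gives both arms the same outcome distribution and the test has its nominal size (loss to follow-up aside). The 8.0% and 2.8% figures require a programme that halves or doubles the variance and leaves the mean where it was. Interval coverage does not need that special null. For the ITT contrast it would be 100 − 8.0 = 92.0% at r = 0.5 and 100 − 2.8 = 97.2% at r = 2, whatever the mean effect. But r itself remains unknown.

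Finally, this is a pilot of preliminary effectiveness with no stated alpha or decision rule. That lowers the stakes. It does not remove the reason to fix the estimator in advance.

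**Conclusion.** The point holds as a cheap improvement. No variance estimator is named, allocation is 2:1, and the default pooled standard errors therefore lack the protection against unequal variances that 1:1 would give. Controlling for baseline does not restore it.

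The size of the error cannot be determined from the documents. It is about 1-3% too large for ITT from the mixture alone (75% adherence and 0.5-1 SD in adherers assumed). Under an assumed twofold variance ratio it is 12% too large with treated women more variable, or 11% too small with controls more variable. These are ratios of variances, not of SDs. Only standard errors, intervals and p-values are affected.

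**What to change.** In SAP 5.1, state that all OLS models use heteroskedasticity-robust standard errors, vce(hc2) or vce(hc3), with one chosen now. Let the same line cover the endline-only models in SAP 7. In SAP 5.2, state that 2SLS uses vce(robust) with the small option.

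The cost is one line in each section and one or two Stata options, with no new data. If the variances are in fact equal, intervals become slightly less stable and, under HC3, slightly wider. Without covariates, HC2 gives s_T²/n_T + s_C²/n_C and HC3 replaces each n by n − 1, so at 160:80 the HC3 standard error exceeds HC2 by at most √(80/79) = 1.006, or 0.6%. The simulation used HC1, so it supports robust errors in general and does not decide between HC2 and HC3.
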